### 6.5 EFFORTS TO MINIMIZE BIAS

Prior to initiation of study participation, each participant who provides informed consent will be assigned a participant number that will serve as the participant identification number on all study documents.

### 7 PARTICIPANT DISCONTINUATION/WITHDRAWAL

A premature discontinuation will occur if a participant who signs informed consent form (ICF) and ceases participation in the study, regardless of circumstances, before the completion of the protocol-defined study procedures.

A participant may withdraw from the study at any time at his/her own request or may be withdrawn at any time at the discretion of the investigator for safety, behavioral, compliance, or administrative reasons.

#### 7.1 PARTICIPANT DISCONTINUATION

Given the nature and design of this study, the reasons for discontinuation are limited.

The investigator should consider withdrawing a participant from the study early if any of the following criteria are met:

- Participant is unwilling or unable to continue to comply with study procedures
- Participant is unwilling or unable to continue in the study

Whenever possible, the decision to withdraw a participant from the study should be discussed with the PIs prior to withdrawal.

If the participant withdraws consent for disclosure of future information, the sponsor may retain and continue to use any data collected before such a withdrawal of consent.

### 7.2 PARTICIPANT WITHDRAWAL

A participant may withdraw from the study:

- at any time at the participant's own request
- at the request of the participant's designee (for example, parents or legal guardian)
- at the discretion of the investigator for safety, behavioral, compliance, or administrative reasons
- if enrolled in any other clinical study involving an investigational product, or enrolled in any other type of medical research judged not to be scientifically or medically compatible with this study

At the time of discontinuing from the study, if possible, the participant will complete procedures for an early discontinuation visit, if applicable, as shown in the SoA.

#### 7.3 PARTICIPANT LOST TO FOLLOW UP

A participant will be considered lost to follow up if he or she repeatedly fails to complete scheduled assessments and is unable to be contacted by the research team.

### 8 STUDY ASSESSMENTS

Study procedures and their timing are summarized in the SoA. Immediate safety concerns should be discussed with the PIs immediately upon occurrence or awareness to determine if the participant should continue or discontinue study intervention. Given this is a non-investigational, observational study, the likelihood of safety concerns is exceptionally low.

Adherence to the study design requirements, including those specified in the SoA, is essential and required for study conduct.

All screening evaluations must be completed to confirm that potential participants meet all eligibility criteria.

### 8.1 PATIENT-REPORTED OUTCOMES

### 8.1.1 Health & Demographics

The Health & Demographics questionnaire is a 20-item assessment that asks participants about their health history and their migraine related medication use. It also asks about participants' gender, race, ethnicity, education, as well as other demographic variables.

A copy of the Health & Demographics items can be found in Appendix B.

#### 8.1.2 MiCOAS Daily Assessment (MiCOAS DA)

The MiCOAS-DA is a *de novo* assessment intended to be completed by participants on a daily (calendar day) basis. The content of the items is spread across 2 general item and 3 individual measures:

- Symptoms (10 items)
- Subjective Mental Acuity (5 items; includes 1 symptom item)
- Physical Function (7 items)

The MiCOAS-DA also includes two general items asking about the participants day with respect to their experience. These two items ("Did you have a migraine day?" and "Did you have a good day?") of the MiCOAS DA use a Yes/No response scale. Nine of the symptom items use a 4-category ordinal response scale, with verbal labels (0 = Did not have to 3 = Severe verbal labels). One symptom item asks which symptom experienced was most bothersome. The remaining 11 non-symptom items use 5-category ordinal response scales, with verbal labels varying depending on item content. Most symptom items use a severity response scale (0 = Did not have to 4 = Severe verbal labels) while the non-symptom mental acuity and function items use a difficulty response scale (verbal labels ranging from 0= Not at all difficult to 4 = Unable to do).

Additionally, MMDs is a common outcome in preventive migraine trials, several other symptom and symptom-related items not included in the MiCOAS-DA based on relevance/importance to patients, such as duration of

head pain, medication use, and unilaterality of pain, are also included in the DA to allow for the identification of a migraine day and, when summarized, the calculation of MMDs.

A copy of the MiCOAS DA items can be found in Appendix C.

#### 8.1.3 MiCOAS Recall-based Measures

The MiCOAS recall-based measures are *de novo* instruments. There are four MiCOAS recall-based measures totaling 32 items:

- Physical function (9 items)
- Subjective Cognition (10 items)
- Social role function (7 items)
- Emotional function (6 items)

Additionally, 4 general function items ("On how many days did you have migraine symptoms?", "How often did you feel good?", "How often were you able to enjoy all or part of the day?", and "How often did you want to spend time alone in a comfortable environment?") are also included. Two versions of the recall-based measures have been created, one with a 7-day recall period and the other with a 14-day recall period (MiCOAS-7 and MiCOAS-14, respectively). The physical function, social role function, and emotional function scale items generally use a 5-category ordinal response scale with frequency labels (i.e., 0 = Never to 4 = Always), while the cognitive function scale items tend to use 5-category ordinal responses with verbal labels on a difficulty scale (i.e., 0 = Not difficult at all to 4 = Unable to do). All MiCOAS scores are calculated such that higher values are associated with more negative outcomes (e.g., worse physical function).

A copy of the MiCOAS Recall-based items can be found in Appendix D. The same set of items are used for the 7-day and 14-day recall.

### 8.1.4 The Migraine Functional Impact Questionnaire (MFIQ)

The Migraine Functional Impact Questionnaire (MFIQ v2; Hareendran et al., 2018; Kawata et al., 2019) is a 26item questionnaire with a 7-day recall period intended to create measures of:

- Physical function (5 items)
- Usual activities (11 items)
- Social function (5 items)
- Emotional function (5 items)

All items use an ordinal, 5-category response scale, with verbal labels varying based on item content. Higher scores on each of the MFIQ domains are associated with worse outcomes (e.g., poorer physical function).

A list of the MFIQ items can be found in Appendix E.

### 8.1.5 The Migraine-Specific Quality of Life Questionnaire version 2.1 (MSQ v2.1)

The Migraine-specific Quality of Life Questionnaire (MSQ v2.1; e.g., Martin et al., 2000) is a 14-item measure with a 4-week recall period intended to assess 3 domains:

- Role function restrictive (7 items)
- o Role function preventive (4 items)
- Emotional function (3 items)

All items use a 6-category ordered response scale with verbal labels ranging from 1 = None of the time to 6 = All of the time. For all three domains of the MSQ v2.1, summed scores from the items contributing to each domain are calculated and then rescaled to a 0 to 100 metric. For all domains, higher scores are associated with better quality of life/outcomes (e.g., fewer role restrictions due to migraine).

A copy of the MSQ v2.1 items can be found in Appendix F.

#### 8.1.6 The 6-item Headache Impact Test (HIT-6)

The 6-item Headache Impact Test (HIT-6; Bayliss & Batenhorst, 2002) is designed to measure the adverse impacts that migraine and headaches have on respondents' lives over the last 4 weeks. All 6 items use a 5-category ordinal response scale with verbal labels ranging from Never to Always. The HIT-6 total score is found as a summed score. The weighting of response options as they contribute to this sum score is as follows: Never (6 points), Rarely (8 points), Sometimes (10 points), Very Often (11 points), and Always (13 points). Rather than using more typical 1 to 5 response-category values, this weighting scheme was empirically determined in the initial publication of the HIT-6 (Kosinski et al., 2003) to maximize the degree to which the HIT-6 summed score mirrored scores derived using IRT estimation and more items from the adaptive administration of the HIT item bank; scores range from 36 to 79 with higher scores indicating greater impact due to migraine/headaches. Thresholds for severity categories have been suggested for the HIT-6 scores (Bayliss & Batenhorst, 2002) which are: 49 or less = Little to no impact; 50-55 = Moderate impact; 56-59 = Substantial impact; and 60 or greater = Severe impact.

A copy of the HIT-6 items can be found in Appendix G.

### 8.1.7 Revised MOS Cognitive Function (MOS-Cog-R) measure

The revised Medical Outcomes Study (MOS) Cognitive Function measure (MOS-Cog-R; Yarlas, White, & Bjorner, 2013) is a 6-item assessment intended to assess cognitive function in adults. The recall period for the MOS-Cog-R is 7 days. The item content of the measure covers such topics as concentration and thinking, confusion, attention, and subjective reaction time. All items of the MOS-Cog-R use a 5-category response scale, with verbal labels ranging from "No time" to "All of the time." A total score is calculated by summing the 6 individual item responses and higher total score values are associated with better cognitive functioning.

A copy of the MOS-Cog-R items can be found in Appendix H.

### 8.1.8 Patient Global Impression of Severity (PGIS)

A patient global impression of status (PGIS) item, asking participants their impression of their migraine severity over the last 7 or 14 days depending on Cohort.

This item can be found in Appendix I.

### 8.1.9 Patient Global Impression of (PGIC)

A patient global impression of change (PGIC) item, asking participants their impression of their migraine severity has changed "since the start of the study."

This item can be found in Appendix J.

### 8.1.10 Monthly Migraine Days

MMD is the number of "migraine days" over the selected 28-day periods. It will be calculated when at least 15 days of the diary are completed out of each 28-day period (through Week 4, Week 5, Day 1 through Week 8). If the number of missing days in the respective 28-day period is > 15 days, MMD will be coded as missing. When the number of missing days in the respective 28-day period is between 1 and 14, a normalization procedure will be applied by multiplying the proportion of migraine days (number of migraine days divided by total number of non-missing days) by 28. For example, if a subject reports 5 migraine days over a total of 20 non-missing diary days, the normalized MMD value would be 7 (i.e., (5/20)\*28 = 7).

The definition of a migraine day will be adapted from the International Headache Society International Classification of Headache Disorders-3 criteria of migraine and current FDA draft guidance (FDA, 2023). Specifically, a qualified migraine day is defined as any calendar day with a headache (head pain of mild, moderate, or severe intensity), with or without aura, lasting for  $\geq$  30 minutes and meeting either of the following criteria (A or B):

- A.  $\geq 2$  of the following headache characteristics:
  - a. Unilateral location
  - b. Pulsating quality (throbbing),
  - c. Moderate or severe pain intensity,
  - d. Aggravation by or causing avoidance of routine physical activity (e.g., walking to climbing stairs)
- B.  $\geq$  1 of the following:
  - a. Nausea and/or vomiting,
  - b. Photophobia
  - c. Phonophobia

Additionally, the use of acute migraine medications to treat head pain of any duration will also be considered a qualified migraine day.

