### 14 APPENDIX C - MICOAS DAILY ASSESSMENT (MICOAS DA)

NOTE: For ease of review, items seen at every administration are presented in **bold**. Items seen based on participant responses/conditional logic are presented in *italics*.

ln '	the past 24 hours
1.	Did you have a good day?  ☐ Yes ☐ No
2.	Did you have a migraine day?  ☐ Yes ☐ No
3.	Did you have a headache or head pain?  □ Did not have □ Mild □ Moderate □ Severe
	3.1 How long did the headache last? [if #3 >= Mild] 30 minutes or less More than 30 minutes but 2 hours or less More than 2 hours but less than 4 hours 4 hours or more
	3.2 Did your head pain get worse with activity [if #3 >= Mild]  ☐ Yes ☐ No
	3.3 Did you have throbbing/pounding head pain? [if #3 >= Mild]  ☐ Yes ☐ No
	3.4 Did you have pain only or worse on one side of your head? [if #3 >= Mild]  ☐ Yes ☐ No
	3.5 Did you take any medication to alleviate your head pain? [if #3 >= Mild]  ☐ Yes ☐ No
	3.6 Did you seek care from a health care provider today because of your headache or head pain? [if #3 >= Mild]  ☐ Yes ☐ No
4	Did you experience any of the following? (check all that apply)  Aura (e.g., visual spots or flashes of light, skin tingling or numbness) [if yes, present 4.1]  Dizziness or vertigo [if yes, present 4.2]  Mental Slowness or Fogginess [if yes, present 4.3]  Nausea [if yes, present 4.4]  Neck Pain [if yes, present 4.5]  Sensitivity to Light [if yes, present 4.6]  Sensitivity to Sound [if yes, present 4.7]  Tired [if yes, present 4.8]  Vomiting [if yes, present 4.9]  None of the above [unavailable to select if any other response is selected; if selected go to #5]

[If YES to corresponding response to #4 present 1 item per screen]

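### The diary items meant to identify a migraine day do not match the protocol's definition, so monthly migraine days can be misclassified to an extent that cannot be estimated

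*Protocol*

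**What the plan says.** Section 8.1.10 defines the unit: "a qualified migraine day is defined as any calendar day with a headache". The headache must last at least 30 minutes and meet criterion A (two or more pain features) or criterion B (nausea and/or vomiting, photophobia or phonophobia). A second route follows: "Additionally, the use of acute migraine medications to treat head pain of any duration will also be considered a qualified migraine day". The count over 28 days is normalized when at least 15 diary days are complete.

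Section 8.1.2 describes the daily assessment as "intended to be completed by participants on a daily (calendar day) basis". It explains that items on duration, medication use and one-sided pain were added so that a migraine day can be identified and MMD calculated.

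Appendix C prints those items:

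- The stem over all daily items refers to "the past 24 hours".
- Item 3.1 (duration) has as its two lowest options "30 minutes or less More than 30 minutes but 2 hours or less".
- Item 3.5 (medication, yes or no) asks "Did you take any medication to alleviate your head pain".

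Section 5.2 says the study length was chosen so that MMD could be calculated and serve as a reference variable. Sections 2.1 and 3.1 say participants are notified when assessments open and when their windows close, but give no hours for the daily diary.

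**The concern.** The definition and the items that must feed it stand in the same protocol and differ on three points: which drugs count, where the duration cut lies, and what a day is. The first two differences are fixed at the moment of data capture. The psychometric analysis plan, due before database lock, can choose a convention. It cannot recover a drug type that was never asked for, or split a response category that was collected whole.

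At stake is the quality of MMD as a yardstick. The medication route bypasses both the duration rule and criteria A and B. If a yes to item 3.5 is taken as the trigger, a brief, mild headache treated with any drug becomes a migraine day. That error would depend on how readily a person treats head pain. It could therefore bias correlations with the new measures, or any MMD-based grouping, rather than merely add noise.

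**Working it through.** **1. The plan's own figure.** MMD = 28 × (migraine days ÷ non-missing diary days). The Section 8.1.10 example gives 28 × 5 ÷ 20 = 7, which reproduces exactly.

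**2. Definition against item.**

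- *Medication.* The definition counts acute migraine medications; item 3.5 counts any drug for head pain. Drug type is not recorded on the day. Appendix B item 6 lists drugs used over the past year, so it cannot settle a given day. If item 3.5 is the trigger, the error is upward or zero.
- *Duration.* The definition needs 30 minutes or more, but item 3.1's lowest option includes exactly 30 minutes. Treating that option as non-qualifying loses a day only if the headache lasted exactly 30 minutes, was untreated, and met A or B. The error is downward or zero.
- *Day unit.* The definition counts calendar days, while the stem covers the preceding 24 hours. No rule assigns an entry to a date. An episode crossing midnight can be moved, counted twice or missed. No direction is fixed.

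The other elements have matching items, except that item 3.2 asks about worsening with activity but not avoidance of it. I leave that aside.

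**3. How many answer patterns are undetermined.** Take a day with head pain: 3 intensities, 4 durations and 7 yes/no answers (worse with activity, throbbing, one-sided, medication, nausea or vomiting, light, sound). That gives 3 × 4 × 2⁷ = 1,536 patterns.

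- Leaving out duration and medication, there are 3 × 2⁶ = 192 feature patterns. Six meet neither A nor B: no B symptom, and either mild pain with at most one other A feature (4 patterns) or moderate or severe pain with none (2 patterns). So 192 − 6 = 186 meet A or B.
- Undetermined through the 30-minute category: lowest duration, no medication, A or B met = 186.
- Undetermined through the medication item: medication yes and not otherwise known to qualify = 192 (lowest duration) + 3 × 6 (longer durations, neither A nor B) = 210.
- The two sets do not overlap: 186 + 210 = 396, and 396 ÷ 1,536 = 26%.

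These are unweighted counts of patterns, not frequencies of days. The 210 falls to zero if the medication term covers every drug taken for head pain.

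**4. Effect of one misclassified day.** The shift is 28 ÷ n, where n is the number of completed diary days:

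- n = 28: 1.00
- n = 20: 1.40
- n = 15 (the minimum): 1.87

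In the protocol's example, one day wrongly added gives 28 × 6 ÷ 20 = 8.4, and one day missed gives 28 × 4 ÷ 20 = 5.6, against 7.

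**The case against.** **A large inflation of MMD.** A reader might infer this by comparing the count under item 3.5 with the days that meet A or B and the duration rule. Assume 12 headache days, 60% of them qualifying and half of the rest treated. The item then gives 7.2 + 2.4 = 9.6 against 7.2, or +33%. That is the wrong comparator, because the definition deliberately counts days treated with acute migraine medication. If a share s of those 2.4 days involved such a drug, the correct count is 7.2 + 2.4s:

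- s = 1: 9.6, no error
- s = 0.8: 9.12, +5%
- s = 0.5: 8.4, +14%
- s = 0: 7.2, +33%

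The documents give no value of s, and every other input here is assumed too. Appendix B accepts over-the-counter drugs as treatment for migraine headaches when they happen, and it lists common analgesics. On that reading s may be near 1. This stands: the text shows a missing definition, not a demonstrated over-count.

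**Several hours of double counting each day.** This might be inferred from the 24-hour stem. It requires completion times scattered over the whole day. Sections 2.1 and 3.1 already provide for assessment windows, and overlaps and gaps balance on average. Only the absence of stated diary hours or a date rule stands.

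**Importance.** Section 9.2 bases the primary analyses on dimensionality and does not mention MMD. Validation also uses MFIQ, MSQ, HIT-6, MOS-Cog-R, PGIS and PGIC. Diary item 2 asks directly whether the day was a migraine day, of participants who say they can tell. This limits the harm but does not remove it, since Section 5.2 names MMD as a reference variable.

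**Conclusion.** The point holds as a mismatch that should be fixed. The daily items cannot implement the Section 8.1.10 definition exactly, so MMD can be misclassified. The documents do not show that it will be misclassified materially, and they do not allow the extent to be estimated. They give no frequency of other drug use for head pain, of headaches lasting exactly 30 minutes, or of episodes crossing midnight.

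The medication mismatch matters most. Its size runs from zero upward and depends entirely on how the undefined term is read. The 30-minute cut is a small boundary issue, and the day unit is a source of error without a known sign. A general statement that MMD is systematically inflated is not supported, since it could apply to only one of the three. The effect per misclassified day, 1.0 to 1.87 on normalized MMD, rests only on the protocol's own formula and its 15-day minimum. The harm is confined to validation analyses that use MMD.

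**What to change.** Reconcile the definition and the items before launch. Which definition of a migraine day is right is not for this review to decide.

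- *Medication.* Either add a drug-type follow-up on days when item 3.5 is answered yes, or define acute migraine medications in Section 8.1.10 so that the term matches what item 3.5 records.
- *Duration.* Make the cut in item 3.1 and the duration rule in Section 8.1.10 the same, by changing either one.
- *Day unit.* State a fixed completion window for the diary, or a rule that assigns each entry to a calendar date.

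Leave the 24-hour stem unchanged. It also governs the scored symptom, mental acuity and physical function items, and altering it would change the recall period of items drafted after cognitive debriefing. Items 3.1 and 3.5 were added for MMD, so editing them does not touch the scored measures.

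The cost is small edits to the electronic diary or the protocol text, at most one extra tap on treated days, and possibly a narrower completion window. If collection has already begun, the drug type and the 30-minute split cannot be recovered for days already recorded. For those days, only aligning the definition to the items remains.

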### 9 STATISTICAL CONSIDERATIONS

### 9.1 STATISTICAL HYPOTHESES

There are no statistical hypotheses regarding efficacy for this study.

### 9.1.1 Multiplicity Adjustment

No adjustments for multiplicity will be included in the analysis.

### 9.2 SAMPLE SIZE DETERMINATION

The primary analyses of concern from this study are the psychometric analyses related to dimensionality, which will be based on modern measurement theory (MMT) analysis techniques such as item factor analysis and analyses from the item response theory (IRT) framework. There are no formal statistical tests that are routinely relied upon in MMT; as such, power analysis or similar to justify the proposed sample size is unavailable. Indeed, MacCallum, Widaman, Zhang, and Hon (1999), after an extensive review of existing recommendations and a large simulation study, stated "that common rules of thumb regarding sample size in factor analysis are not valid or useful. The minimum level of N, or the minimum N:p ratio, needed to assure good recovery of population factors is not constant across studies, but rather is dependent on some aspects of the variables and design in a given study." (P. 96) Based on their simulation results and making a recommendation for a worst-case scenario factor analysis, MacCallum and colleagues stated samples well over 500 will be necessary. The proposed completion sample of approximately 1000 participants is well over this minimum and should be of appropriate size for the planned analyses. Further, given that item factor analysis and IRT have been demonstrated to be equivalent models (e.g., Takane & De Leeuw, 1987; Wirth & Edwards, 2007), any sample size requirements sufficient for factor analysis will also be appropriate for the application of IRT analysis methods.

